4.10.3.2. Standard of Care Dressing

The Aquacel® Ag Surgical or other equivalent dressing may be replaced as needed for the duration of the treatment period. Total treatment time should be no shorter than five days post-surgery and should not exceed the maximum number days indicated in the IFU document included with the dressing applied immediately following surgery.

4.10.3.3. Documentation

The following information regarding the application of study treatments will be documented after the surgery:

- Date of removal
- SOC only
- The number of dressing replacements
- Type of dressing (if any) applied after removal of study treatment
- ciNPT only
- Replacement of therapy unit
- Number and dates of dressing replacements (Prevena™ Peel & Place™ or Prevena Plus™ Customizable™)
- Type of dressing (if any) applied after removal of ciNPT

4.11. Post-Operative Assessments

4.11.1. Investigator-Assessed Surgical Site Complication (SSC)

The Investigator will examine the subject and the surgical incision at the scheduled assessment visits – Weekly, Midterm Follow-up, and Long Term Follow-up – as well as any unscheduled visits initiated by the subject or the Investigator. The Investigator will evaluate the subject for all complications at each visit, regardless if the subject has a documented SSC event.

For all SSC events, the date of onset will be recorded. Not all reported adverse events that are surgical complications will meet the criteria for an SSC event.

Subjects with a documented SSC event will continue to be assessed through the Long Term Follow-up visit or study withdrawal and all newly occurring complications will be recorded.

4.11.1.1. SSC Components

1. Superficial Incisional Surgical Site Infection (SSI) involves only skin and subcutaneous tissue of the incision and meets at least one of the following criteria:
 - purulent drainage from superficial incision;
 - organisms identified from an aseptically-obtained specimen from the superficial incision or subcutaneous tissue by a culture or non-culture based microbiologic testing method which is performed for purposes of clinical diagnosis or treatment (e.g., not Active Surveillance Culture/Testing [ASC/AST]);
 - both of the following:
 - superficial incision that is deliberately opened by Investigator and culture or non-culture based testing is not performed, and
 - at least one of the following signs or symptoms:
 - pain or tenderness;
 - localized swelling;
 - erythema; or
 - heat.
 - diagnosis of superficial SSI by the Investigator.
2. Deep Incisional SSI which involves deep soft tissue of the surgical incision, occurs within 90 days after the revision, and has at least one of the following:
 - purulent drainage from the deep surgical incision;
 - both of the following:
 - a deep incision that spontaneously dehisces, or is deliberately opened or aspirated by the Investigator and organism is identified by a culture or non-culture based microbiologic testing method which is performed for purposes of clinical diagnosis or treatment (e.g., not Active Surveillance Culture/Testing (ASC/AST) or culture or non-culture based microbiologic testing method is not performed:
 - at least one of the following signs or symptoms:

- fever(>38°C);
- localized pain, or
- tenderness.

Note: A culture or non-culture based test that has a negative finding does not meet this criterion.

- an abscess or other evidence of infection involving the deep incision that is detected on gross anatomical or histopathologic exam, or imaging test.
3. Full thickness skin dehiscence, defined as a separation of the closed incision at least through the subcutaneous tissue or deeper and at least one mm wide.
 4. Seroma or hematoma requiring drainage or surgery. The fluid accumulation will be classified as hematoma (bloody fluid) or seroma (clear or serous fluid) after drainage. The drainage may be percutaneous, an open technique at the bedside, or open surgical drainage.
 5. Skin necrosis is defined as the presence of necrotic tissue/skin eschar at the incision site that requires intervention with antibiotics, excision, and/or re-operation.
 6. Continued drainage determined by an Investigator's visual inspection of the incision after completion of the study treatment period and removal of the study treatment dressing.

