All subjects must receive ciNPT for a duration consistent with the IFU document included with the selected Prevena[™] Dressing but no shorter than five days post-surgery. A maximum duration indicated in the IFU document of the Prevena[™] Dressing applied immediately following surgery is encouraged. The dressing should not be lifted or removed for reasons other than those related to the device such as initial malfunction or leak alarm.

At the end of the ciNPT treatment period, the dressing and unit are to be removed; re-application of the Prevena[™] dressing is prohibited after the treatment period. If continued drainage is determined by the Investigator's visual inspection of the incision at the time of dressing removal, an SSC event should be documented.

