4.11.1.3. Special Reporting Instructions for Continued Drainage

It is typical for a closed incision to drain up to 72 hours after surgery. However, if the closed incision continues to drain at the time of dressing removal (> 5 days) as determined by the Investigator to require significant medical intervention, then the occurrence will be

documented as an SSC. Investigators will assess any signs of infection, including purulent discharge or pus, for an SSI and document accordingly.

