4.11.2. Intervention Assessment

Information related to all interventions that are performed for an SSC will be documented at all post-surgery visits including unscheduled visits. Information collected will include but is not limited to:

- Date of intervention
- Type of interventions
- Types of interventions may include open surgical or percutaneous drainage, debridement, excision, or re-operation.

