4.15. Prohibited Procedures and Treatments

Subjects who undergo a subsequent surgery involving the initial TKA incision within 90 days must withdraw from the study.

Subjects who receive a subsequent TKA revision on the same knee within 90 days of the study revision must withdraw from the study prior to the procedure. Sites will record any SSCs that occur prior to the subsequent TKA revision and document the revision as the reason for the withdrawal from the study.

In the absence of an SSC, subjects receiving cross-over therapy after completing the original study treatment (ie, therapy from the arm in which the subject was not initially treated) must withdraw from the study.

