8. STATISTICAL CONSIDERATIONS

8.1. Endpoint Definitions for Analysis

8.1.1. Primary Endpoint – Subject Incidence SSC

The primary endpoint is the incidence of surgical site complications (SSCs) within 90 days of TKA revision in subjects treated with ciNPT as compared to standard of care surgical dressing. The SSC endpoint includes any occurrence of superficial SSI, deep SSI, dehiscence, seroma, hematoma, skin necrosis, or continued drainage as outlined in section 4.11.1. For this endpoint there are three possible outcomes:

- “Occurred”, which is assigned if the subject had one or more occurrences of any complication and the onset date of the complication was between the time of the TKA revision and not later than 90 days after;
- “No occurrences”, which is assigned if the subject had no known occurrences of a complication within 90 days of the TKA revision and was assessed at least once on or after the 90th day following the TKA revision;
- “Incomplete follow-up”, which is assigned if the subject had no occurrences of the complication within 90 days of the TKA revision and did not have an assessment at least 90 days after the date of the revision surgery.

If a subject experiences one occurrence of any of the six complications, the primary outcome will be considered “Occurred”.

For each component of the SSC, the start date of the complication will be recorded in order to calculate the number of days from the revision surgery until occurrence of the event. If the complication did not occur, the number of days will be calculated using the last assessment which confirmed the subject to be complication-free.

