4 STUDY ENDPOINTS

4.1 Primary Endpoint

The primary endpoint is the subject incidence of Investigator-assessed surgical site complications (SSCs) within 90 days of TKA revision in subjects treated with ciNPT as compared to standard of care (SOC) surgical dressing. SSCs include any occurrence of superficial surgical site infection (SSI), deep SSI, dehiscence, seroma, hematoma, skin necrosis, or continued drainage as outlined in Section 4.11.1 of the study protocol. Three possible values for the primary endpoint are:

- “Occurred”: If the subject had one or more occurrences of SSC on or before 90 days post TKA revision;
- “No occurrences”: If the subject had an assessment of SSC on or after 90 days post TKA revision and had no known occurrence of any SSC within 90 days of the TKA revision.
- “Incomplete follow-up”: If the subject had no known occurrences of SSC and did not have any SSC assessment at least 90 days post TKA revision.

The start date of the complication will be recorded in order to calculate the number of days from the revision surgery until occurrence of the event.

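### Continued drainage, one of six primary-endpoint components, is defined with an intervention threshold in one section and without it in two others

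*Protocol*

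**What the plan says.** Four Protocol sections bear on when drainage is an SSC.

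- **4.11.1.1 item 6** defines it by the Investigator's "visual inspection of the incision after completion of the study treatment period and removal of the study treatment dressing". No intervention is required.
- **4.10.3.1** (ciNPT removal) says that if drainage is found on "visual inspection of the incision at the time of dressing removal, an SSC event should be documented". Again there is no condition.
- **4.11.1.3** (special reporting instructions) makes drainage at dressing removal an SSC only "as determined by the Investigator to require significant medical intervention", and adds in parentheses that removal is later than five days.
- **4.10.3.2** (standard-of-care removal) gives no drainage instruction. It says "Total treatment time should be no shorter than five days post-surgery".

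The endpoint definitions do not choose between these. Protocol 8.1.1 lists "skin necrosis, or continued drainage as outlined in section 4.11.1"; SAP 4.1 lists "skin necrosis, or continued drainage as outlined in Section 4.11.1 of the study protocol". Protocol 8.1.1 makes a subject *Occurred* on a single event of any of the six components. The trial is open-label, the endpoint is Investigator-assessed, and the documents describe no blinded adjudication of SSCs.

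**The concern.** The two rules classify the same subject differently, and the person choosing between them knows the treatment arm. If rule use differs between sites or arms, the primary comparison mixes a treatment effect with a classification effect.

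A second route runs through Protocol 4.15, which requires withdrawal for the following group: "In the absence of an SSC, subjects receiving cross-over therapy after completing the original study treatment". A subject with low-grade drainage who then receives the other arm's therapy stays in the study under the broad rule. Under the strict rule the subject must withdraw, becomes *Incomplete follow-up* if no other SSC was recorded, and drops out of the mITT set on which the primary test is run.

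The direction of any bias is unknown. The prompt to document drainage at removal appears only in the ciNPT section, so if it is acted on more there it counts against ciNPT. Discretion over the threshold could go either way.

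**Working it through.** **The rules side by side**, for a subject with visible drainage at dressing removal, no intervention judged significant, and no other SSC:

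| Section | Condition | Subject is |
|---|---|---|
| 4.11.1.1 item 6 | seen on inspection after removal | *Occurred* |
| 4.10.3.1 (ciNPT only) | seen on inspection at removal | *Occurred* |
| 4.11.1.3 | must require significant intervention | *No occurrences* |

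Items 4 (seroma or hematoma) and 5 (skin necrosis) carry their intervention requirement inside the definition; item 6 does not. The SAP 8.5.1 summary of SSCs that required intervention includes drainage, but it also lists those two components, which require intervention by definition. It therefore does not show which rule was meant. Timing is also loose: removal on day 5 satisfies the minimum in 4.10.3.2 but is not later than five days as 4.11.1.3 has it.

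**The plan's own figure.** Protocol 8.4.2 assumes SSC rates of 33% (septic) and 6.9% (aseptic) with half the subjects septic: 0.5 × 0.33 + 0.5 × 0.069 = 0.1995, stated as 20%. For 20% against 10%, two-sided 0.05 and 80% power:

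n = [1.960 × √(2 × 0.15 × 0.85) + 0.842 × √(0.16 + 0.09)]² / 0.10² = 199 per arm, as stated.

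**Sensitivity to the rule.** The documents give no drainage rate, so the shifts below are assumptions. Power is exact: the sum of Bin(a; 199, p₁) × Bin(b; 199, p₂) over all outcomes (a, b) with |z| ≥ 1.977 (two-sided 0.048), where z = [(a − b)/199] / √(2p̄(1 − p̄)/199) and p̄ = (a + b)/398. This is the unstratified chi-square test with the interim look ignored, as an approximation to the stratified CMH test. Base case, 20% against 10%: 0.80.

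*If the 20% excludes low-grade drainage and the broad rule adds it to the standard-of-care rate:*

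| Points added (subjects of 199) | No ciNPT effect on drainage | ciNPT halves drainage |
|---|---|---|
| 2.5 (5) | 22.5 vs 12.5%: 0.75 | 22.5 vs 11.25%: 0.86 |
| 5 (10) | 25 vs 15%: 0.70 | 25 vs 12.5%: 0.90 |
| 10 (20) | 30 vs 20%: 0.63 | 30 vs 15%: 0.95 |

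Power stays at 0.80 when the drainage risk ratio is 0.76, 0.78 or 0.80 for the three rows respectively.

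*If the 20% already includes such drainage and the strict rule removes it:*

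| Points removed | Remaining events halved by ciNPT | No ciNPT effect on the removed events |
|---|---|---|
| 2.5 | 17.5 vs 8.75%: 0.74 | 17.5 vs 7.5%: 0.86 |
| 5 | 15 vs 7.5%: 0.66 | 15 vs 5%: 0.93 |
| 10 | 10 vs 5%: 0.47 | not meaningful (would leave 0% on ciNPT) |

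**If the arms are classified by different rules.** With a true rate of 20% in both arms and one arm's recorded rate lowered by 2 or 5 points, the same calculation gives a two-sided rejection rate of about 0.08 or 0.25, against a nominal 0.048. This is a conditional risk, not a forecast.

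**The case against.** The best counter-reading is that item 6 says how drainage is detected and 4.11.1.3 says when it is reported. 4.11.1.3 is headed as a special reporting instruction, sits inside the section that both endpoint definitions cite, and stands next to 4.11.1.2, which narrows superficial SSI in a similar way. That may well be the intent. But no text says that item 6 is qualified, and the reading does not dispose of 4.10.3.1, whose instruction to document an SSC is unconditional.

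Other points stand in part:

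- **Arm asymmetry.** Protocol 4.11.1 requires assessment for all complications at every visit, and 5.1 and 5.2.4 place SSC assessment at the dressing-removal visit for all subjects. Both rules thus apply to both arms; only the written prompt is one-sided.
- **Meaning of intervention.** Protocol 4.11.2 lists example intervention types, so there is a starting point, but it does not say which are significant.
- **Cross-over route.** It needs a chain of events whose frequency is unknown. It is a possible path, not a demonstrated one.
- **Size.** The 10-point removal is extreme. In the retrospective series described in Protocol 1.3, comparator wound complications were 26.9% and SSIs 18.5%. If each patient counts once, 8.4 points are non-SSI, or 8.4 × 20/26.9 = 6.2 points on a 20% rate, shared among several complication types. That series mixed hips and knees and is not named as the source of the 20%, so this is only indicative.

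**Conclusion.** The concern holds and should be fixed before lock. Two incompatible rules define an event in the primary endpoint, the SAP does not choose between them, and the assessor is unblinded. This conclusion rests on the text alone.

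The size and direction of the effect are unknown. The power range (0.47 to 0.95; 0.66 to 0.93 for shifts of up to 5 points) rests on assumed drainage rates, 199 evaluable subjects per arm and an unstratified single-look test. It shows that the choice of rule can matter, not that power is lost. The five-day timing mismatch is minor.

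**What to change.** 1. Reconcile Protocol 4.10.3.1, 4.10.3.2, 4.11.1.1 item 6 and 4.11.1.3 into one drainage definition and one timing rule, worded identically for both arms, with the same documentation prompt in both removal sections. The sponsor chooses the rule before database lock and without results by arm; this review does not propose the threshold or the day. If the rule refers to intervention, define the term.
2. At dressing removal, record for every subject whether drainage is present (yes/no, date), separately from whether intervention was required. Protocol 4.11.2 does not cover this: "Information related to all interventions that are performed for an SSC will be documented", so drainage not called an SSC leaves no entry there.
3. Add to SAP 8.5.1 two stratified CMH sensitivity analyses of the SSC composite: one under the definition not chosen and one with drainage excluded. Re-derive the mITT set each time, because membership under SAP section 5 depends on having an SSC. The by-type repeats in Protocol 8.3.4 and the by-type, intervention and drainage-to-SSI summaries in SAP 8.5.1 do not re-form the composite.

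The cost is a protocol clarification, one case report form field (if none exists; the form is not in the documents) and two SAP tables. The real downside is retrospective: drainage judged below the threshold may never have been recorded, and site queries may be incomplete and would be answered by unblinded staff. Checking adverse event records first limits this, since Protocol 4.11.1 expects some surgical complications to be reported as adverse events without being SSCs. Where such drainage cannot be recovered, the alternative-definition analysis should be reported as incomplete.

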4.11.1.2. Special Reporting Instructions for Superficial SSI

Assessments of SSI will follow the CDC classification of superficial infections.¹⁷ Specifically, the following do not qualify as criteria for meeting the National Healthcare Safety Network (NHSN) definition:

- Diagnosis/treatment of cellulitis (redness/warmth/swelling), by itself, does not meet the last criterion for superficial incisional SSI. Conversely, an incision that is draining or that has organisms identified by culture or non-culture based testing is not considered a cellulitis.
- A stitch abscess alone (minimal inflammation and discharge confined to the points of suture penetration).

4.11.1.3. Special Reporting Instructions for Continued Drainage

It is typical for a closed incision to drain up to 72 hours after surgery. However, if the closed incision continues to drain at the time of dressing removal (> 5 days) as determined by the Investigator to require significant medical intervention, then the occurrence will be

documented as an SSC. Investigators will assess any signs of infection, including purulent discharge or pus, for an SSI and document accordingly.

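### The continued-drainage rules contradict each other at a compliant day-5 dressing removal, and only the ciNPT removal section tells the Investigator to record drainage as an SSC

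*Protocol*

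**What the plan says.** **Treatment duration.** Protocol 4.10.3.1 requires ciNPT for a period consistent with the instructions for the "selected Prevena[™] Dressing but no shorter than five days post-surgery". Protocol 4.10.3.2 says of the SOC dressing: "Total treatment time should be no shorter than five days post-surgery". Removal on day 5 is therefore compliant in both arms.

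**Drainage at removal, ciNPT.** Section 4.10.3.1 adds that if continued drainage is found on "visual inspection of the incision at the time of dressing removal, an SSC event should be documented".

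**Drainage at removal, SOC.** Section 4.10.3.2 covers dressing replacement and treatment time. It does not mention drainage or an SSC.

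**Component definition, both arms.** Item 6 of 4.11.1.1 rests on the Investigator's "visual inspection of the incision after completion of the study treatment period and removal of the study treatment dressing".

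**Reporting instruction, both arms.** Section 4.11.1.3 covers the case "if the closed incision continues to drain at the time of dressing removal (> 5 days", and adds that the drainage must persist "as determined by the Investigator to require significant medical intervention".

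**Endpoint.** Under Protocol 8.1.1 a single occurrence of any of the six complications classifies the subject as having the primary event. SAP 4.1 takes the definition from Protocol 4.11.1, which contains both the component definition and the reporting instruction.

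**The concern.** A dressing taken off on day 5 has been worn for the permitted minimum, but five days is not more than five days. A site with a draining incision at that visit can record an SSC by following one section, or record nothing by following another, and be within the protocol either way.

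The removal sections add a difference between arms. A site that turns to the removal instructions finds an order to document an SSC for a ciNPT subject and finds nothing for an SOC subject. It is then left with 4.11.1, where the two rules disagree. The trial is open-label, the Investigator makes the assessment, the documents describe no adjudication, and the removal day is at the site's discretion within the permitted window. At stake is comparable ascertainment of one component of the primary composite.

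**Working it through.** **Step 1: the rules side by side for drainage seen at a day-5 removal.**

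| Protocol section | Applies to | Day limit | Intervention condition | Counts at day 5? |
|---|---|---|---|---|
| 4.11.1.1, item 6 | both arms | none | none | yes |
| 4.10.3.1 | ciNPT | none | none | yes |
| 4.10.3.2 | SOC | no drainage rule | no drainage rule | silent |
| 4.11.1.3 | both arms | more than 5 days | yes | not covered |

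Permitted removal is day ≥ 5; the reporting instruction covers day > 5. The two differ at day 5 only. The intervention condition separates 4.11.1.3 from 4.11.1.1 and 4.10.3.1 on every removal day, so it is probably the larger inconsistency.

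**Step 2: the plan's own figure.** Inputs from Protocol 8.4.2: SSC rates 20% and 10%, two-sided alpha 0.05, power 80%.

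n = [1.960·√(2·0.15·0.85) + 0.842·√(0.20·0.80 + 0.10·0.90)]² / 0.10² = (0.990 + 0.421)² / 0.01 ≈ 199 per arm, which matches the plan. The planned difference is 199 × 0.20 − 199 × 0.10 = 39.8 − 19.9 = 19.9 events.

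**Step 3: illustrative size.** The documents give neither the drainage rate at removal nor the distribution of removal days. Assume 3-8% of subjects drain at removal and 10-30% of removals fall on day 5 or earlier, independently of drainage.

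- Low: 199 × 0.03 × 0.10 = 0.6 subjects per arm (0.3%).
- High: 199 × 0.08 × 0.30 = 4.8 subjects per arm (2.4%).

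This treats every such subject as changing status. Some would not: drainage may persist to a later visit, another component may already have occurred, or the site may apply 4.11.1.1.

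**Step 4: effect on the comparison.** With n = 199 per arm and final alpha 0.048 (z = 1.977):

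power = Φ{[d − z·√(2p̄(1−p̄)/n)] / √([p₁(1−p₁) + p₂(1−p₂)]/n)}

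- As planned (20.0% v 10.0%): Φ[(0.100 − 1.977 × 0.0358)/0.0354] = 79.5%.
- Uncounted in SOC only, because sites follow 4.10.3.1 for ciNPT and 4.11.1.3 for SOC: 19.7% v 10.0% gives 77.4%; 17.6% v 10.0% gives 58.8%. The observed difference falls from 10 points to between 9.7 and 7.6.
- Uncounted in both arms, in proportion to their event rates, at the high end: 17.6% v 8.8% gives 73.3%.
- Uncounted in ciNPT only: the observed difference rises to between 10.3 and 12.4 points.

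The direction depends on site behaviour. The removal sections as written point to the SOC-only case, which works against ciNPT.

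**The case against.** The strongest reply is that 4.11.1.1 holds the endpoint definition, applies to both arms and has no day limit, while 4.11.1.3 is only a reporting note. Section 4.11.1.2 lists findings that do not qualify as superficial SSI; 4.11.1.3 never says that day-5 drainage is not an SSC. The figure in brackets may simply restate the five-day minimum loosely. This stands to the extent that a reader might infer that day-5 drainage is excluded from the primary endpoint, and the documents do not support that. They contradict each other and name no rule that prevails. Read loosely, the bracket still misdescribes a compliant day-5 removal.

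A reader might also infer that dressings will come off before day 5 because of heavy drainage, and that those events are lost. The documents do not support this either. Ending treatment early is a deviation. The ciNPT dressing is not to be lifted except for device reasons, and an SOC replacement during treatment is not the end of treatment. SAP 8.7.7 has a duration convention for treatment ending on the day of surgery, but this does not show how often that happens or why. Protocol 4.11.1 requires evaluation for all complications at every visit, and the schedule in 5.1 has SSC assessments at end of treatment, midterm and long-term follow-up, so persisting drainage can still be recorded.

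Finally, the arms share 4.11.1.1 and 4.11.1.3, so they do not have different endpoint definitions. That is correct. The difference is an instruction present in one removal section and absent from the other. In an unblinded, Investigator-assessed endpoint it is still worth removing.

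**Conclusion.** The wording is wrong as it stands. At a compliant day-5 removal, 4.11.1.1 and, for ciNPT, 4.10.3.1 count drainage as an SSC, while 4.11.1.3 does not cover it, and neither the protocol nor the SAP settles the matter. Only ciNPT sites are told in the removal section to document the event.

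The size is unknown and probably small. The range of 0.6 to 4.8 subjects per arm, and the power figures derived from it, rest wholly on assumed rates and on every affected subject changing status. They show what could happen; they do not predict bias in a given direction. Section 4.10.3.1 encourages the maximum duration for ciNPT, which argues against many day-5 removals in that arm, but 4.10.3.2 has no matching encouragement, so removal days could differ between arms. The sample size reproduces and is not in question. The change is worth making because it costs almost nothing and removes an arm-dependent ambiguity from the primary endpoint.

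**What to change.** - Reconcile 4.10.3.1, 4.10.3.2, 4.11.1.1 item 6 and 4.11.1.3 into one continued-drainage definition for both arms. Any day limit in it should include every removal day that the treatment rule permits.
- Put the same removal-visit drainage instruction, word for word, in 4.10.3.1 and 4.10.3.2.
- For a dressing removed earlier as a deviation, state that drainage is classified at the next SSC assessment already required by 4.11.1.
- In the same edit, settle whether the intervention condition, which appears only in 4.11.1.3, belongs to the definition, and state it once.

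Treatment duration does not change. The cost is protocol and eCRF-guideline wording, with no new visits, procedures or subjects.
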